### **7.4.2 Analysis of Secondary Endpoints**

#### **7.4.2.1 Cancer Biopsy Incidence and Secondary Rise in PSA**

The incidence of negative biopsy for cancer and secondary rise in serum PSA will be summarized with frequencies and percentages at one and two years by treatment group, subgroups and overall.

Treatment comparisons will be performed using the exact binomial distribution as well as the normal approximation to the binomial distribution. Inferences will include 95% confidence intervals of the odds ratio for each endpoint between treatment groups at both Year 1 and Year 2 for biopsies and for each of Years 1 and 2 and end of study for PSA. Comparison between enzalutamide and AS will be evaluated by logistic regression using the treatment groups, randomization stratification factors [prostate cancer risk (low/intermediate), type of biopsy performed (mpMRI targeted/non mpMRI targeted)], age, race, and time since prostate cancer diagnosis as fixed effects and site and subject as random effects.

Time to PSA progression will be analyzed with the same methods as detailed for the primary endpoint analysis in Section 7.4.1.

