### 7.4.1 Analysis of Primary Endpoint(s)

The primary efficacy endpoint is time to prostate cancer progression (pathological or therapeutic), and the hypothesis for analysis is:

$H_0$ : The time to progression for Enzalutamide and Active Surveillance (AS) are the

same  $H_1$ : The time to progression for Enzalutamide and AS are not the same

Median and 95% confidence intervals for time to prostate cancer progression (pathological or therapeutic) will be calculated with the Kaplan-Meier (KM) method for each treatment group. Subjects with no cancer progression at the time of trial completion, discontinuation or death will be censored at the last assessment date. Additionally, subjects switching therapy during the study will be censored at the time of the initial therapy switch, but subjects discontinuing therapy will not be censored until the time of study discontinuation. If less than 50% of subjects progress by study cut-off time, the 25th percentile and its two-sided 95% confidence interval will be reported. KM plots will be generated.

Treatment group differences between enzalutamide versus AS will be based on a Cox regression model. The resulting Hazard ratio (enzalutamide/AS) and 95% confidence interval will be included in the summary. Censoring assumptions will follow the same rules as applied for the KM estimates. Fixed effects for the model will include the treatment groups, randomization stratification factors [prostate cancer risk (low/intermediate), type of biopsy performed (mpMRI targeted/non mpMRI targeted)], age, race, and time since prostate cancer diagnosis. Additionally, a random effect of site will be included in the model.

The association between the survival time, log of time to disease progression, and survival probability, log negative log, will be investigated graphically by Cox proportional-hazards models. If the proportional hazards assumption is violated, appropriate remedial methods will be investigated and applied.

Data listings will be provided.

In addition to an overall analysis, the primary and secondary analyses will be repeated for pathological progression and therapeutic progression, individually.

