#### 7.4.1.1 Secondary Analyses

The incidence of subjects with prostate cancer progression (pathological or therapeutic) will be summarized with frequencies and percentages at one year, two years, and study completion. Treatment group differences will be assessed using a logistic regression with the same covariates and random effect used in the primary analysis and include two-sided 95% confidence interval estimates of the odds ratio.

In addition to an overall analysis, the primary and secondary analyses will be repeated for pathological progression and therapeutic progression, individually.

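### The adjusted logistic model for negative biopsy and PSA rise has a subject random effect but no time or time-by-treatment term, so it cannot give adjusted odds ratios at Year 1, Year 2 or, for PSA, end of study

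*SAP*

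**What the plan says.** SAP section 7.4.2.1 covers two binary secondary endpoints, negative biopsy and secondary rise in PSA. Both are tabulated by arm at one and two years. Three analysis statements follow in this order:

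- The two-group methods come first: "Treatment comparisons will be performed using the exact binomial distribution as well as the normal approximation to the binomial distribution".
- The estimates required are then set out as "95% confidence intervals of the odds ratio for each endpoint between treatment groups at both Year 1 and Year 2 for biopsies". PSA rise is to be compared at the same two years and once more when the study ends.
- The adjusted model is named last: "Comparison between enzalutamide and AS will be evaluated by logistic regression using the treatment groups, randomization stratification factors". It also adjusts for age and race, and its list of terms closes with "time since prostate cancer diagnosis as fixed effects and site and subject as random effects".

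The covariate list has no term for time point and no interaction of time with treatment. The section does not say whether the model is fitted to all time points together or to each one separately.

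Two other models in the SAP are specified differently. Section 7.4.1.1 analyses progression incidence by "logistic regression with the same covariates and random effect used in the primary analysis", and section 7.4.1 gives that effect as site alone: "Additionally, a random effect of site will be included in the model". Section 7.4.2.3, the repeated-measures model for percent positive cores, has a subject effect and also lists time and its interaction with treatment. Section 8 records site as an added random effect but does not mention subject.

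**The concern.** A subject random effect belongs in a model with repeated outcomes per man. Such a model needs time terms if the treatment effect is to be reported by time point. Section 7.4.2.1 has the subject effect without the time terms, so the listed model fits neither a joint nor a per-time-point analysis.

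Timing matters in this design. Section 3.2 gives one year of treatment, a further year of follow-up, and biopsies at 12 and 24 months. The Year 1 biopsy therefore describes the end of treatment and the Year 2 biopsy describes a year off treatment. A single treatment coefficient assumes that the odds ratio is the same at both. At stake is the covariate-adjusted estimate at each time point for two secondary endpoints. Leaving the choice to the programmer also leaves an analytic decision open in an open-label trial.

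**Working it through.** The SAP states no rate, odds ratio or power for these endpoints, so there is no figure to reproduce. The check is structural, with illustrations. All rates and standard deviations (SDs) below are assumptions; only N = 222 at 1:1 comes from the SAP (section 4).

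**Reading 1: all time points in one model, as listed.** The linear predictor is intercept + β × treatment + covariates + site + subject. There is one β, hence one odds ratio, whatever the number of time points. For two years, the common value can be approximated from proportions averaged over the years, using OR = [p1/(1 − p1)] / [p0/(1 − p0)], with p1 for enzalutamide and p0 for active surveillance.

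Assume Year 1 is 35% v 14%, so OR = (0.35/0.65)/(0.14/0.86) = 3.31. Then vary Year 2:

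| Year 2 assumption | Year 2 OR | Averaged rates | Common OR |
|---|---|---|---|
| Same as Year 1, 35% v 14% | 3.31 | 35% v 14% | 3.31 |
| Midway, 25.5% v 15% | 1.94 | 30.25% v 14.5% | 2.56 |
| No effect, 16% v 16% | 1.00 | 25.5% v 15% | 1.94 |

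The last row is (0.255/0.745)/(0.15/0.85) = 1.94. The midway row takes Year 2 rates halfway between the other two rows: (35 + 16)/2 = 25.5 and (14 + 16)/2 = 15.

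A simulation of the mixed model agrees with the last row. It used 222 men, two outcomes each, subject SD 1.0, true subject-level odds ratios of 3.5 at Year 1 and 1.0 at Year 2, and 60 trials, without covariates or site. The model as listed gave a median odds ratio of 1.96, which describes neither year.

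**Reading 2: a separate fit at each time point, as listed.** Each man now contributes one 0/1 outcome. The likelihood depends on the subject effect only through the averaged probability for his covariate values. Any subject SD can be offset by rescaling the coefficients. In one simulated Year 1 data set, with the SD held fixed at different values:

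| Subject SD | Maximised −log L | Treatment OR |
|---|---|---|
| 0.01 | 132.48966 | 2.38 |
| 0.5 | 132.48966 | 2.49 |
| 1 | 132.48966 | 2.80 |
| 2 | 132.48966 | 3.99 |
| 4 | 132.48966 | 9.86 |

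The fit is identical throughout while the odds ratio moves from 2.38 to 9.86. With covariates the likelihood need not be exactly flat, but the only information on the SD would then come from the shape of the link function, not from replication within men. The reported odds ratio would depend largely on how the software handles that parameter.

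**After repair, in the same simulation.** Adding year and year-by-treatment and keeping the subject effect gave median odds ratios of 3.43 and 1.00, against a truth of 3.5 and 1.0. Separate yearly models without the subject effect gave 2.83 and 1.00 on the population-averaged scale. Either repair gives time-specific estimates.

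The end-of-study PSA comparison has the same structure and the same fault.

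**The case against.** The strongest reply is that the year-specific odds ratios were never meant to come from the logistic model. The sentence requiring them, "between treatment groups at both Year 1 and Year 2 for biopsies", directly follows the exact and normal-approximation methods, and the logistic model comes afterwards in a sentence that names no year. That reading is natural, and it stands in part: the binomial comparisons can supply unadjusted year-specific odds ratios, and the percentages are tabulated by year.

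A reader might therefore infer too much from the gap, namely that the report would hide whether a Year 1 difference persists at Year 2. The document does not support that, because the tabulations and unadjusted comparisons would show it. A reader might also treat the difference in scale between a subject-specific and an unadjusted odds ratio as an error. It is not: a subject-specific odds ratio is a legitimate target, and any covariate-adjusted model with a site effect already departs from the unadjusted scale.

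Two further points are fair. The contrast of a large Year 1 effect with none at Year 2 is close to the worst case for a common odds ratio. A programmer might also simply fit per year and drop the subject effect. That would work, but it departs from the listed model.

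The reply does not repair the logistic model itself. The unadjusted results omit the stratification factors, covariates and site that the SAP chose to adjust for, and nothing elsewhere in the SAP supplies the missing time terms or removes the subject effect.

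**Conclusion.** The point holds for the adjusted logistic model only. As listed, it gives one common odds ratio if fitted jointly and has an unidentifiable subject variance if fitted per time point. On neither reading does it give an adjusted odds ratio at Year 1, Year 2 or, for PSA, end of study.

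The size cannot be fixed from the SAP. With the assumed Year 1 rates, the common odds ratio runs from 3.3 (no distortion, equal effects in both years) to about 1.9 (no effect at Year 2). These are secondary endpoints in a study that describes itself as exploratory, and neither the primary Cox analysis nor the progression-incidence model in section 7.4.1.1 is affected. The model should be corrected, but the trial's main conclusion does not depend on it.

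**What to change.** Amend section 7.4.2.1 to one of the following:

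1. Fit a separate logistic model at each time point (Year 1, Year 2, and end of study for PSA) with the listed fixed effects and a site random effect, and no subject effect. This matches the random-effect structure in section 7.4.1.1.
2. Fit one repeated-measures logistic model with time point (categorical) and time-by-treatment terms added. Report the odds ratio and 95% confidence interval at each time point, and state whether they are marginal or subject-specific.

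In either case, say which analysis supplies the reported time-specific odds ratios, and label the binomial comparisons as unadjusted. The cost is SAP wording and programming; no data collection or design feature changes.

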#### **7.4.2.2 Brief Fatigue Inventory**

The Brief Fatigue Inventory (BFI) is a questionnaire that assesses tiredness, fatigue, ability to perform general activities, mood, walking ability, interaction with others, etc. using 9 questions, assessed at Randomization, 3, 6, 12, 18, and 24 months. The answers range from “0 – minimal/does not interfere” to “10 – severe/completely interferes.” Standard composite scores and change from baseline at each time point will be summarized with descriptive statistics by treatment group, stratification factors [prostate cancer risk (low/intermediate) and type of biopsy performed (mpMRI targeted/non-mpMRI targeted)], subgroups (age, race, and BMI at Screening) and overall. Composite scores for all licensed instruments will be calculated per the licensing agreements.

When there are missing data, if half or more questions within scale are answered then a score will be calculated for that scale. Otherwise the patient score for that scale will be missing. For single-item measures, a missing score will not be imputed.

BFI compliance and completion rates at each visit will be calculated using the following definitions:

- BFI compliance rate: will be defined as the proportion of patients who completed the PRO instrument among those who were expected to complete at each visit, excluding those missing by design (e.g. death, discontinuation of treatment, or no visit scheduled).

- BFI completion rate: defined as the proportion of patients who completed the PRO instrument at baseline and  $\geq 1$  assessment subsequently among those who completed PRO baseline and are remaining in study at each follow up timepoint.

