7. Clinical labs, which will be assessed by the study's central laboratory, include serum chemistries (comprehensive metabolic panel) and hematology (CBC with differential).
8. Serum hormonal levels to be measured are testosterone, DHT, dihydroepiandrosterone, androstenedione and estradiol.
9. Serum PSA will be measured by the study's central laboratory.
10. If warranted per Investigator's clinical opinion or per standard of care.
11. [REDACTED] **CCI** [REDACTED].
12. Biopsies may be done with or without mpMRI targeting. Sites must use a consistent method (either with or without mpMRI targeting) for all of their study subjects. Any biopsy performed during the subject's study participation will be analyzed centrally (for histological reading, [REDACTED] **CCI** [REDACTED]).
13. Biopsy must be done within 6 months prior to the Screening Visit, and submitted for central analysis (histological reading, [REDACTED] **CCI** [REDACTED]). For this biopsy, a minimum of 10 cores is required.
14. Subjects who withdraw from the study prior to the 24m Visit will be asked to complete all subject reported outcomes questionnaires (BFI, SF-12, EPIC, MAX-PC) at their final study visit.
15. Only the urinary, sexual and hormonal domains will be used.
16. Adverse events (serious and non-serious) will be collected from the time the subject signs the consent form until the subject completes the study.
17. Study drug is only applicable to subjects randomized to the enzalutamide arm; subjects randomized to AS will not be dispensed any study drug.
18. Subjects will have the option of having an additional sample collected at each phlebotomy session for storage and analysis in future trials of future trials of biomarker discovery for localized prostate cancer

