**CCI**

#### **3.2 Study Design**

This is a multicenter, randomized, open label exploratory study, conducted in the US and Canada, evaluating the efficacy and safety of enzalutamide for extension of time to prostate cancer progression (pathological or therapeutic) in subjects with clinically localized, histologically proven prostate cancer that is categorized as low risk or intermediate risk and who are under AS. A total of 222 subjects from approximately 50 centers will be enrolled. Subjects are eligible if they were diagnosed within 6 months of screening and have been on AS. A minimum of ten cores from transrectal ultrasound-guided prostate biopsy (mpMRI targeted versus non-mpMRI targeted) are required; confirmatory biopsy before entering the study is not required and is done at the discretion of the investigator.

Low risk is defined as T1c-T2a, PSA $<$ 10, N0, M0 (or presumed N0, M0 if computerized tomography [CT]/bone scan not done due to low risk of metastases), GS  $\leq$  6, ECOG status  $\leq$  2 and estimated life expectancy  $>$  5 years. Intermediate risk is defined as T2b-T2c, PSA $<$ 20, N0, M0 (or presumed N0, M0 if CT/bone scan not done), GS  $\leq$  7 (3+4 pattern only), ECOG status  $\leq$  2 and estimated life expectancy  $>$  5 years.

Prostate cancer progression is defined as either therapeutic progression or pathological progression. Therapeutic progression is defined as the earliest occurrence of primary therapy for prostate cancer (prostatectomy / radiation / focal therapy / systemic therapy). Pathological progression is defined as increase in primary or secondary Gleason pattern by  $>$  1 or higher

proportion of cancer positive cores (>15% increase). Subjects will be stratified by low versus intermediate risk and type of biopsy performed (mpMRI targeted versus non-mpMRI targeted).

Subjects will be randomized (1:1) either to receive treatment with enzalutamide (160 mg), administered as four 40 mg capsules, by mouth, once daily or to AS during the one year study treatment period. Following the one year treatment period, all subjects will be followed for one additional year. Subjects will be followed up every 3 months for these 2 years, after which follow-up will either be every 6 months or unscheduled until the last subject finished their 2 year follow-up. Serum PSA will be measured at baseline and every 3 months during subsequent follow-up visits.

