Digital rectal examination will be done at baseline and every 6 months during subsequent follow-up visits. All subjects will have transrectal ultrasound-guided prostate biopsy (with or without mpMRI targeting) at 12 months and 24 months with a standard of 12 cores required; two biopsies are required from each target site (if mpMRI is used) as well as 12 systematic biopsies (12 core transrectal ultrasonography [TRUS] guided systematic biopsies including six lateral and six mid lobar cores from the base, middle and apex of the gland) at the same time. All sites will be consistent with their method of biopsy (with regards to the use of mpMRI targeting) throughout the study for all subjects enrolled at that site. If there is a significant clinical reason such as adverse changes on digital rectal examination or increase in PSA, biopsy is allowed based on investigator's decision. If at any time during the study the subject considers intervention for prostate cancer, biopsy is allowed and recommended.

Treatment decisions based on pathological progression are at the discretion of the individual investigator. Hormonal levels (testosterone, DHT, dihydroepiandrosterone, androstenedione and estradiol) will be collected at baseline, 12 months and 24 months. Quality of life/sexual function questionnaires (EPIC), anxiety measures (MAX-PC), BFI, SF-12 assessments will also be done at baseline, 6 months, 12 months, 18 months and 24 months. An additional BFI assessment will be done at 3 months. Subjects who withdraw from the study before the 24 Month visit will be asked to complete the EPIC, MAX-PC, BFI and SF-12 assessments at their final study visit.

Subjects will be followed beyond the two year study period until the last subject has completed the 24 month visit. This additional follow up will entail biannual visits (every 6 months and/or unscheduled visits) that include measurement of serum PSA and digital rectal exam.

All biopsy samples, including those collected for-cause or per standard of care, will be centrally read by a designated pathologist blinded to treatment allocation. CT, magnetic resonance imaging (MRI) and bone scan will be performed at the discretion of the investigator based on clinical need; when performed, these assessments will be read locally and recorded in the electronic case report form (eCRF).

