Progression-free survival is defined as the time (in months) from the date of randomization until the date of the cancer progression (pathological or therapeutic). Pathological progression is defined as increase in primary or secondary Gleason pattern by  $\geq 1$  or higher proportion of cancer positive cores ( $\geq 15\%$  increase). Therapeutic progression is defined as the earliest occurrence of primary therapy for prostate cancer (prostatectomy/radiation/focal therapy/systemic therapy).

Subjects with no cancer progression at the time of trial completion (the last study-wide subject completes a 24 month follow-up visit), discontinuation or death will be censored at the last assessment date. Subjects discontinuing therapy will not be censored until the time of study discontinuation. Additionally, subjects switching therapy during the study will be censored at the time of the initial therapy switch.

For subjects on enzalutamide, TEAEs, defined as an adverse event observed after starting administration of the study drug and until 30 days after treatment end date, are categorized as AEs. If the adverse event occurs on Day 1 and the onset check box is marked “Onset after first dose of study drug” or the onset check box is left blank, then the adverse event will be considered treatment emergent. If the adverse event occurs on Day 1 and the onset check box is marked “Onset before first dose of study drug”, then the adverse event will be categorized as medical history. If a subject experiences an event both during the pre-investigational period and during the investigational period, the event will be considered as an AE only if it has worsened in severity (i.e. it is reported with a new start date). All adverse events collected that begin within 30 days following study discontinuation will also be counted.

Percent positive cores are calculated using the number of systemically-sampled prostate regions and any targeted regions with at least one positive core divided by the total number of systematically-sampled regions and targeted regions. This implies that despite the number of samples within a given systematic or targeted region, any positive core will indicate that region as positive.

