#### **7.4.2.4 SF-12**

The Medical Outcomes Study 12-Item Short Form Survey (SF-12) is a questionnaire that measures overall health related quality of life using 12 questions, assessed at Randomization, 6, 12, 18, and 24 months. Summation of standardized questions' scores are used to calculate the PCS and MCS Composite Scores. Scores and change from baseline will be analyzed at each time point and overall in the same manner as the BFI scores. To distinguish clinically meaningful differences from statistically significant differences, the minimum clinically important difference (MCID) will be calculated using a distribution-based approach as 0.5 baseline score standard deviation pooled over treatment groups for each domain. Equivalence will be demonstrated when the entire 95% confidence interval for the adjusted mean difference or change is within the range from  $-MCID$  to  $+MCID$ .

Similar to BFI, SF-12 compliance and completion rates will be calculated at each visit.

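### The PRO completion rate is not tied to the visit it is reported for, and the PRO compliance rate leaves out men who stopped treatment but still owe questionnaires

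*SAP*

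**What the plan says.** SAP Section 7.4.2.2 introduces the rates with: "BFI compliance and completion rates at each visit will be calculated using the following definitions".

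- **Compliance** is the share who completed the instrument among those expected to do so at the visit, "excluding those missing by design (e.g. death, discontinuation of treatment, or no visit scheduled").
- **Completion** is the share with a baseline form and at least one "assessment subsequently among those who completed PRO baseline and are remaining in study at each follow up timepoint".

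The other instruments inherit these definitions. Section 7.4.2.4 states "Similar to BFI, SF-12 compliance and completion rates will be calculated at each visit". Section 7.4.2.5 says the same for EPIC. So does Section 7.4.2.6 for MAX-PC, although its sentence ends by naming the EPIC assessments.

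On who is due a form, Section 3.2 says the questionnaires "will also be done at baseline, 6 months, 12 months, 18 months and 24 months", with an extra BFI at 3 months. It also says: "Following the one year treatment period, all subjects will be followed for one additional year". Section 6.4 says: "Subjects discontinuing therapy will not be censored until the time of study discontinuation". Footnote 14 to Table 2 asks for all questionnaires at the final visit even from men who leave the study before month 24. Footnote 17 says "subjects randomized to AS will not be dispensed any study drug".

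**The concern.** A rate reported by visit should say how many of the forms due at that visit came back. Neither rate does so.

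The completion numerator refers to any later form, so the rate cannot fall because of forms missed after a man's first post-baseline one.

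Compliance is specific to the visit, but it classes treatment discontinuation with death and unscheduled visits as a reason why no form was due. The follow-up rules say otherwise: stopping treatment does not end a man's participation or his questionnaire schedule. A form he misses afterwards was due and is missing.

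Section 7.10.1 analyses available data with no general imputation, so readers will use these rates to judge how far the PRO summaries can be trusted. Men who stop a drug early may differ in fatigue or hormonal symptoms from those who continue, and theirs are the missing forms that the compliance rate leaves out.

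**Working it through.** The SAP states no PRO compliance or completion figure, so there is nothing to reproduce. The two definitions can be applied to assumed values.

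**Inputs from the SAP.** 222 men randomized 1:1 (Section 4), so 222/2 = 111 per arm; five post-baseline BFI visits at 3, 6, 12, 18 and 24 months (Section 7.4.2.2).

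**Assumptions (not in the SAP).** All 111 enzalutamide men complete baseline and remain in study. A share d is off drug: 5%, 10%, 20% or 30%. Return is 90% on drug and r off drug, with r = 50% as the central case and 30% and 90% as the range.

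**Compliance.**

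- True visit rate = 0.9(1 − d) + r·d.
- SAP rate, reading A (all off-drug men excluded) = 0.9.
- SAP rate, reading B (only off-drug men with no form excluded) = [0.9(1 − d) + r·d] / [(1 − d) + r·d].

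Example, d = 30% and r = 50%: on drug 77.7, off drug 33.3. Forms returned = 77.7 × 0.9 + 33.3 × 0.5 = 69.93 + 16.65 = 86.58. True rate = 86.58/111 = 78.0%. Reading A = 69.93/77.7 = 90.0%. Reading B = 86.58/(77.7 + 16.65) = 91.8%.

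| Off drug (r = 50%) | True rate | Reading A | Reading B | Overstatement A / B (points) | Missing forms left out |
|---|---|---|---|---|---|
| 5% | 88.0% | 90.0% | 90.3% | 2.0 / 2.3 | 2.8 |
| 10% | 86.0% | 90.0% | 90.5% | 4.0 / 4.5 | 5.6 |
| 20% | 82.0% | 90.0% | 91.1% | 8.0 / 9.1 | 11.1 |
| 30% | 78.0% | 90.0% | 91.8% | 12.0 / 13.8 | 16.6 |

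With r = 30%, the true rate runs from 87.0% down to 72.0%, so reading A overstates by 3 to 18 points. With r = 90%, the true rate is 90.0% throughout: reading A is unbiased, and reading B is too high by 0.5 to 2.8 points.

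In the AS arm the same exclusion changes nothing if no AS man can be classed as having discontinued treatment. The SAP does not say whether one can.

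**Completion.** Suppose return over the five BFI visits falls 95%, 85%, 70%, 60%, 50%, with the same men stopping for good while staying in study. The SAP rate is 95% at every visit. If instead returns are independent between visits at 70%, the share with at least one form by the k-th visit is 1 − 0.3^k: 70%, 91%, 97.3%, 99.2%, 99.8%, against a true 70% each time. Read literally, a form returned after the visit being reported would count as well. This applies equally to both arms, and the denominator does keep off-drug men who remain in study.

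**The case against.** Several objections are sound and limit the point.

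- **Other outputs show the loss.** Score summaries by time point carry n (Sections 7.1 and 7.4.2.2), Section 7.4.2.6 promises PRO listings by treatment group and visit, and Section 7.2.1 tabulates disposition. A reader might infer that the two rates are the only check on missing PRO data; they are not.
- **Compliance is visit-specific.** A poor month-24 return would show in that rate even where completion reads high. Only the treatment-discontinuation exclusion can mask missing forms there.
- **The arm difference comes from compliance alone.** A reader might attribute it to both rates, but the completion numerator works the same way in each arm.
- **An effect in AS is not ruled out.** Section 6.4 starts a treatment phase at randomization for AS, Section 7.10.1 refers to the end of one year of surveillance, and Section 7.2.1 counts treatment discontinuation by treatment group. It would go too far to say that AS is unaffected.
- **Planned completion is probably not discontinuation.** Section 7.2.1 separates the two, so the SAP does not support reading the exclusion as removing every enzalutamide man after month 12.
- **A reversed arm comparison is not shown.** It would require an AS return rate that the SAP does not give.
- **The consequence is limited.** Section 8 restricts PRO analysis to descriptive statistics, and the rates enter no estimate or test.

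None of this makes the definitions right. A completion rate labelled by visit still does not describe that visit, and men who owe a form are still left out of compliance.

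**Conclusion.** The point holds as a defect of definition in two rates, carried across four instruments. The completion fault follows from the wording and acts in both arms. The compliance fault follows from setting the exclusion beside the SAP's own follow-up rules; it probably acts mainly in the enzalutamide arm, because only that arm is dispensed study drug.

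The size cannot be derived from the SAP. With 5-30% off drug, 90% return on drug and 50% off drug, enzalutamide compliance is overstated by about 2 to 12 points when all off-drug men are excluded (about 2 to 14 when only those with a missing form are). It is about 0 to 3 points if off-drug men return forms as often as others. What is at stake is how the PRO results are interpreted; the primary endpoint is untouched. This is a minor point that is worth correcting.

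**What to change.** For BFI, SF-12, EPIC and MAX-PC, by arm and visit:

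- **Compliance:** forms completed at that visit, divided by men alive, in study and due a form at that visit, whatever their treatment status. Remove treatment discontinuation from the reasons for a form being missing by design.
- **Completion:** men with a baseline form and a form at that visit, divided by men with a baseline form who remain in study at that visit.
- If a count of men with baseline plus at least one later form is wanted, report it once as an evaluability count, not by visit.

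Correct the MAX-PC sentence in the same edit so that it names its own instrument. The cost is SAP wording and the matching table programming; no new data are needed. The downside is that reported rates may be lower.
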